Sponsor	Northern Care Alliance NHS Foundation Trust Sponsor representative: [name], Head of Research Research and Innovation Northern Care Alliance NHS Foundation Trust [name] [contact]
Funder(s)	No grant funding – [name] - PI account
Key Protocol Contributors including statistical support	[name] Consultant Rheumatologist [contact] [name] Statistician [contact]

ROLE OF STUDY SPONSOR

Northern Care Alliance NHS Foundation Trust assumes overall responsibility for the initiation and management of the study. The sponsor has delegated responsibility to the Chief Investigator for study design, conduct, data analysis and interpretation, manuscript writing, and dissemination of results.

ROLES AND RESPONSIBILITIES OF STUDY MANAGEMENT COMMITEES

Trial Management Group to oversee proceedings.

[name] - Consultant Rheumatologist and Chief Investigator

[name] - Clinical Scientist

[name] - Senior Vascular Technician

[name] - Study Co-ordinator)

[name] - Deputy Research and Innovation Manager

Short title/acronym: Light treatment for scleroderma finger ulcers - study 2

Patient & Public Involvement Group

To recruit 2 patients from Salford Royal Hospital with systemic sclerosis (SSc), to provide feedback on patient facing documents and relevance of study to patients with SSc.

1 Study Summary

Study Title	A physiological study to optimise a novel low-level light treatment for digital ischaemia in patients with systemic sclerosis
R&I Reference	24MSK13-S
Research Question/Aim(s)	 Primary Aim: To assess the safety, tolerability, and efficacy (as assessed by surrogate measurement of skin perfusion and temperature) of our low-level light therapy (combined red, infrared and violet wavelength). concerning dose finding with lower and higher irradiances, including evidence of a biphasic response with higher irradiance dose. Secondary Aim: To investigate potential SSc patient- and disease-related factors relevant to cutaneous irradiation with low-level light therapy (LTTT). Age and disease duration. Skin thickness.
Study Participants	Patients with SSc
Planned Size of Sample	20
Planned Study Period	Study start date: 14/02/2025 Recruitment end date: 13/02/2026 Final study end date: 20/02/2026

2 Lay Summary

Digital (finger) ulcers are common in patients with systemic sclerosis (SSc) otherwise known as scleroderma and many of the current treatments used can cause side effects or are not effective. We want to investigate a novel light-based therapy to potentially treat digital ischaemia (low blood flow) that causes digital ulcers.

In our previous study, our custom-built light-based treatment device, consisting of red, infrared, and violet wavelengths was found to be safe and feasible. There were also some early signals of potential benefit for digital ulcers in patients with SSc. To take this treatment approach forward, we now need to refine the optimal 'dose' of light.

Participants wishing to take part will need to attend Salford Royal Hospital for three study visits. At the first visit the research team we will examine the participant's fingers and back of their hands for any skin thickness changes (gently pinching the skin) as is routinely performed in the scleroderma outpatient clinic. Skin thickness will also be measured at these sites using an ultrasound machine.

At each visit, participants will receive one of three randomised 'doses' of the combination light therapy. The research team wishes to understand how the skin (blood flow and temperature) reacts to increasing dose of light. All patients will receive the three 'doses' of light over the three study visits (but not all in the same order), there is no placebo treatment. The light application to the skin will take approximately 15 minutes to complete.

We will measure the blood flow and temperature of the skin immediately before, directly after, and then every 10 minutes for 90 minutes after the light therapy. These will be measured using a type of scanner called 'laser Doppler imaging' and a thermal camera, which will each take approximately 1 minute (or less) per scan.

3 Background

Systemic sclerosis (SSc) is a complex autoimmune connective tissue disease characterised by microvascular abnormalities, fibrosis of the skin and internal organs, and immune system activation [1]. Digital ulcers (DUs) are common in patients with SSc and are responsible for much of the pain and disability associated with the disease [2,3].

SSc-Digital Ulcers (DUs)

Half of patients with SSc report a history of DUs, often occurring early in the course of the disease [4]. DUs, in particular those located on the fingertip, are believed to be ischemic in aetiology [5]. Patients with SSc also commonly have marked finger contractures, which may predispose to recurrent trauma and can make wound care challenging for patients [6].

Despite there being systemic (pharmacological) therapies available to prevent and treat intercurrent DUs [7], recurrent ulceration remains a major source of morbidity in some patients with SSc [8,9]. Furthermore, DUs are often superficially infected, in particular, with Staphylococcus aureus [10], and can undergo deeper bony progression. Unfortunately, despite targeted intervention, in some patients, digital amputation may be necessary for refractory DUs.

There are limited data concerning the local (wound) management (non-surgical and surgical) for SSc-DU [11–13]. However, there is strong expert opinion favouring the local treatment for SSc-DU, which would likely be better tolerated by patients (e.g., through the absence of significant vasodilatory side effects from systemic therapies) and could potentially be administered in the community (e.g., avoiding the cost, and inconvenience to patients themselves, associated with the need for hospitalisation). To this end, a number of other local

approaches to DU treatment have been suggested to have potential benefit [11–13]. However, the current evidence in SSc is still very limited and does not strongly support any specific local treatment.

Low-level light treatment for cutaneous ulceration

Low-level light therapy (LLLT) is an area of growing clinical interest. While its use has been largely empirical and complicated by the application of various wavelengths and dosimetric parameters, it is now reported in a number of studies (albeit with a lack of any high-quality randomised controlled trials) to be a safe and effective treatment for refractory skin (diabetic, pressure, and venous) ulcers [14]. In summary, the majority of previous studies have reported that LLLT was associated with around an additional 50% (range of 30–60%) in improvement in ulcer status compared with the comparator group (conventional wound care and/or placebo light treatment) [14–24].

Light treatment within the red and near-infrared spectrum is believed to stimulate a wide number of cellular processes (often referred to as 'biostimulation') which are thought to benefit wound healing, including (but not limited to) stimulation of fibroblast and macrophage number and function, increasing leucocyte mobility, modulation of growth factors and inflammatory mediators, and by promoting collagen deposition and neovascularisation [25,26].

Infrared light is also associated with ambient heating and an increase in blood flow (although this is likely short-lived), and improved tissue oxygenation. Red light can also have an antimicrobial effect through excitation of naturally occurring porphyrins (30). In a blinded, randomised, placebo-controlled, single treatment trial, photodynamic therapy with red light and an exogenous photosensitiser caused a significant reduction in bacterial load of diabetic ulcers, and a trend toward ulcer healing [27].

Violet light also has an antibacterial effect including activity in vitro against Staphylococcus aureus [28]. Impact of the LLLT may occur both via effects on the ulcer bed and on the ulcer margins, including with respect to bacteria present. While blue light can reach bacteria residing on the surface or within the epidermis, bacteria can also colonize deeper dermal components of the skin, and blue light will be less effective than red/infrared in reaching these. DUs in patients with SSc are relatively superficial, with an average depth of 1 mm (as measured by high-frequency ultrasound); therefore, this is unlikely to be an important disadvantage [29]. While there is much less of a precedent for the use of violet (or blue) light to treat ulcers, it is important to consider that blue light is more photochemically active than red light and causes more reactive oxygen species generation [30]. Blue light has been shown to increase perfusion through stimulation of local nitric oxide (NO) release, with relaxation of vascular smooth muscle, and to increase wound healing in a skin excision model [31].

LLLT for SSc-DUs

We have previously developed at Salford Royal Hospital a custom-built LLLT device comprising infrared (850 nm), red (660 nm), and violet (405 nm) LEDs was utilized (Figure 1).

[figure not shown]

Figure 1. LLLT for SSc-related DUs. A: Side profile of the light device. B: The light device in operation treating an extensor aspect DU in a patient with SSc. The distance from the panel of LEDs to the treatment area is approximately 15 cm.

Unlike previous studies, all three specifically chosen wavelengths were given simultaneously. SSc-DUs were irradiated with 10 J/cm² twice weekly for 3 weeks, with follow-up at weeks 4 and 8 [32]. Any safety concerns were documented. Patient opinion on time to deliver, feasibility, and pain visual analogue score (VAS; 0-100, 100 most severe) was collected. Patient and clinician DU global assessment visual analogue score (VAS) were documented. DUs were evaluated by laser Doppler perfusion imaging pre- and post-irradiation. In all, 14 DUs in eight patients received a total of 46 light exposures, with no safety concerns. All patients considered LTTT 'took just the right amount of time' and was 'feasible', with a low associated mean pain VAS of 1.6 (SD: 5.2). Patient and clinician global DC VAS improved during the study (mean change: -7.1 and -5.2, respectively, both p <0.001). DU perfusion significantly increased post-irradiation.

Recently, Spinella et al [33], report their positive preliminary evaluation of the role and effectiveness of blue light photobiomodulation therapy with EmoLED® for scleroderma skin ulcers (SU). The authors retrospectively analysed 12 consecutive patients with a total of 15 SU on finger hands. All patients were treated with adequate systemic therapy and local treatment for SU; after a standard skin ulcer bed preparation with debridement of all lesions, EmoLED® was performed. All patients were locally treated every week during 2 months of follow-up; and SU data were collected after 4 weeks (T4) and 8 weeks (T8). Eight SSc patients with comparable SU were also evaluated as controls. The application of EmoLED® in addition to debridement apparently produced faster healing of SU. Complete healing of SU was recorded in 41.6% cases during EmoLED® treatment. Significant improvements in SU area, length, and width, wound bed, and related pain were observed in EmoLED® patients from T0 to T8. Control subjects treated with standard systemic/local therapies merely showed an amelioration of SU area and width at the end of the follow-up. No procedural or post-procedural adverse events were reported.

Rationale for further development of our novel LLLT for SSc-DU

Our previous feasibility study demonstrated that our novel LTTT for DUs was safe, feasible, and well tolerated. Furthermore, there was an early tentative suggestion of treatment efficacy. There is a significant therapeutic rationale to develop locally acting treatments for SSc-DU, which likely would be better tolerated by patients, and could be administered potentially in the community (our outpatient setting under medical supervision), thereby avoiding the costs and inconvenience from inpatient hospitalisation. Furthermore, many previous studies have found comparable efficacy at lower doses (total dose 5 to 10 J/cm²). Although, some studies have also found positive results with much higher doses, such as 20J/cm², 70J/cm², or even higher.

However, a biphasic response to light is well known, and therefore there is a need to scientifically determine the dose-ranging of LLLT for SSc-DU, including examination of potential patient- and disease-related factors.

4 Objectives

Primary Objective: To assess the safety, tolerability, and efficacy (as assessed by surrogate measurement of skin perfusion and temperature) of our LLLT (combined red, infrared and violet wavelengths) concerning dose finding with lower and higher irradiances, including evidence of a biphasic response with higher irradiance dose.

Secondary Objective: To investigate potential SSc patient- and disease-related factors relevant to cutaneous irradiation with LTTT.

- Age and disease duration.
- Skin thickness.

5 Study Design

A physiological, clinical laboratory-based, study of LLLT.

LTTT experimental setup

A new LTTT device (Figure 2) shall be constructed in-house by Medical Physics at Salford Royal Hospital and subject to appropriate safety and quality assurance checks.

Allocation of LLLT intervention

Prior to the initial study visit, an independent member of the study team shall perform the randomisation procedure. Randomisation to be done in house by study team (e.g., using random number generator/excel). All patients shall receive combined sequential red (810nm)/infrared (850nm) followed by blue (410nm) wavelengths. The dose per visit shall be dose-escalated in a pre-determined randomised order over the course of the three study visits: 5 J/cm² or 10 J/cm² (i.e., the dose of our previously explored LLLT), and 20 J/cm²

Figure 2. New LED experimental setup for our proposed laboratory-based study. Left: LED array (Hogga) to deliver red (660nm) and near-infrared (850nm) light – the same as utilised in our previous study. Right: LED device (Hogga) to deliver blue (415nm) light (very similar to our previous study – 405nm).

A custom-built configuration shall allow irradiation of the participants fingers/hands. The wavelengths shall be delivered sequentially to the patient's treated hand (i.e., red/infrared and then blue light). Similar to our previous study, we envisage that a future LTTT device would uniquely combine and deliver all three wavelengths simultaneously. However, for our planned experimental approach by using available LED-based light systems, this will enable us to achieve the intended aims of our study and is significantly less expensive than constructing a new custom-built treatment device.

Participation

Taking part is voluntary and it is up to patients to decide whether or not to take part. If they decide to take part, they are free to withdraw at any time without giving a reason. A decision to withdraw at any time will not affect their standard of any care they receive. If they do wish to withdraw, they simply need to inform a member of the research team and they will cancel any planned future visits. Any images and data collected up to the point of withdrawal will be retained by the research team for use in the study.

Participant will potentially be in the study for up to 7 days. If they lose capacity for any reason during that time they will be withdrawn from the study and no further study visits will take place. Any images or data collected before the participant in question lost capacity would be retained for use in the study analysis.

Study visit protocol

Participant progression throughout the study is presented in Figure 3. Study visits will be conducted in a temperature-controlled (at 23°C) laboratory at Salford Royal Hospital. Patients will attend a total of 3 study (morning) visits over 3 (ideally consecutive) days. The minimum time between study visits is 1 day, and the maximum time between study visits shall be 3 days. Patients can attend consecutive days because there is not expected to be any significant carry-over therapeutically relevant effect from the LLLT. Relevant patient-and disease-related demographics and characteristics shall be collected. At each study visit, any relevant change/s to current drug treatment will be documented.

Participants will not be paid to take part in the study; however, they will be reimbursed reasonable travelling expenses for each of their 3 study visits

[figure not shown]

Figure 3. Participant progression throughout the study. We assume no significant therapeutic carry over effect between the LLLT irradiation between study visits (minimum of 24 hours).

Preparation

Patients will be asked to abstain from caffeine-containing drinks and from smoking for at least 4 hours prior to study.

Clinical data

After signing the informed consent form, the patient will be interviewed by a member of the study team using a standard proforma and/or standardised proformas.

This will include:

- Demographic information.
- Gender.
- Age.
- Smoking status
- Fitzpatrick skin type/colour (for potential effects of melanin).
- Modified Rodnan skin score assessment
- Current medication/s.
- Past medical history.
- Disease-related history (e.g., history of severe digital vascular disease).
- Record of ulcers present and past and also of location, duration etc.
- Handedness (i.e., dominant hand).

Application of the LLLT device

We will apply the LLLT (for all study visits) to the dominant hand unless there are specific reasons not to, which will be documented. For example, due to patient preference or major musculoskeletal involvement with upper limb disability/contractures prohibiting correct positioning for the application of the LLLT.

Both the patient and device operator/s will wear appropriate safety goggles (as advised by Medical Physics at Salford Care Royal Hospital) at all times whilst the LLLT device is in operation. The patient will place their hand within the treatment area of the light-based device (total treatment area of approximately 15cm²), aiming to centralise the hand (fingers/thumbs and dorsal aspect) within the treatment region. The device will be directly controlled by an attached custom-built computer interface. At each study visit, the device will undergo a period of automatic calibration before use.

Using the custom interface/s, the dose of the wavelengths can be selected to be delivered as prior study. The dose will be delivered either at 5 J/cm², 10 J/cm² or 20 J/cm² based upon the patient study visit sequence/randomisation. The LLLT will take approximately 10-15 minutes to complete.

Outcome measures

Assessment of safety and tolerability

At each treatment study visit any safety issues (between visits) will be documented (e.g., new concerns about cutaneous changes). This will be documented on a separate safety CRF at visits 2 and 3 (attached with this application). Patient reported pain on a VAS scale (0-100, where 100 is the most severe pain imaginable by

the patient) directly attributed to the LLLT will be recorded immediately after treatment, on a separate tolerability CRF at visits 1, 2 and 3 (attached with this application), to assess tolerability, at each study visit.

Assessment of efficacy

Laser Doppler imaging (LDI); LDI which measures blood flow allows a perfusion map (in arbitrary units) to be produced of the studied area. We will perform LDI immediately before and after the light exposures and then every 10 minutes for 90 minutes. LDI will include all the digits (thumb and four fingers) and dorsum of both the *treated* and *untreated* hands. Bilateral (matching) standard regions of interest (ROI) shall be assessed on the treated and untreated hands all LDI time points. The rationale of imaging these sites is to demonstrate an objective *localised* increase in skin perfusion with light treatment, and whether this differs between the digits and dorsum of the hand.

Thermography: Thermographic assessment measures skin temperature and provides an indirect measure of small and large blood vessel function and can also be applied to SSc-DUs. Standardised thermographic images shall be acquired immediately before and after the light exposures, and then every 10 minutes for 90 minutes. As for LDI, thermography will simultaneously image the whole treated hand to capture the fingers and dorsal aspect, and with contralateral counterparts on the untreated hand.

Assessment of persistent cutaneous digital ischaemia

Taken from the hand original acquired LDI and thermography images (as above), for any digital (finger) ulcers (DU) or pitting scars (DPS) present, perfusion measurements will be assessed at the lesion center (DU/DPS 'core') and immediately adjacent tissue (DU/DPS 'periphery').

Assessment of digital skin fibrosis:

Rodnan skin score: By a trained assessor using the modified Rodnan skin score by manual palpation (0-3 score, where 0 is normal and 3 is severe skin fibrosis/sclerosis).

High frequency ultrasound (HFUS): HFUS imaging (Episcan I-200, frequency 35 MHz) will be performed (using sterile ultrasound gel) along the visually apparent mid-point of the proximal and middle phalanges. From, this the HFUS images can be used to markup and extract measures of skin thickness (averaged per hand and individual proximal and middle phalanges).

6 Recruitment

Twenty patients > 18 years of age with SSc-spectrum disorders will be recruited. Patients with SSc will be prospectively recruited at Salford Royal Hospital either at their routine clinic attendance or through contacting patients who have previously given their permission to be contacted about future relevant studies.

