7.2 Statistical Analyses

To assess tolerability of irradiance wavelengths, VAS scores will be graphically explored. To observe the change over time, area under the curve will be calculated for each patient to estimate the blood flow/temperature, and a t-test will be used to test for differences. Our physiological study data shall inform the sample size calculation of a future feasibility RCT. However, in our previous investigation, which included eight patients (with 14 SSc-DU), we observed

an increase in perfusion of 15-32% post-irradiation with LTTT. We shall perform tentative analyses to explore the impact of our specified patient- and disease-related factors.

The study team including [name], [name], [name] and [name], will be responsible for transcribing, coding, de-identifying, storing/transferring, accessing and archiving study data.

8 Regulatory and Ethical Considerations

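### The allocation rule in Section 5 calls the dose order both escalated and randomised; randomised orders are meant, so the escalation term should go and the permitted orders should be stated

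*Protocol*

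**What the plan says.** The allocation rule in Protocol Section 5 reads "The dose per visit shall be dose-escalated in a pre-determined randomised order over the course of the three study visits", and then lists 5, 10 and 20 J/cm². The same paragraph says that, before the first visit, "an independent member of the study team shall perform the randomisation procedure". It mentions a random number generator or Excel only as an example and does not say whether the orders are balanced.

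Elsewhere the protocol describes randomised order alone. The Lay Summary says that each visit delivers one of three randomised doses and that every patient receives all three, "but not all in the same order". Under Application of the LLLT device in Section 5, the dose at a visit is "based upon the patient study visit sequence/randomisation".

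The Background reports the team's earlier study, in which "SSc-DUs were irradiated with 10 J/cm² twice weekly for 3 weeks". The rationale that closes the Background says that "there is a need to scientifically determine the dose-ranging of LLLT for SSc-DU".

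For the analysis, Section 7.2 computes an area under the curve per patient for blood flow and temperature, after which "a t-test will be used to test for differences". It does not mention visit.

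**The concern.** Escalation means an ascending dose, whereas a randomised order lets any dose come first. One sentence cannot prescribe both, and this sentence is the operative rule from which the allocation list will be made.

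If it were carried out as escalation, every patient would have 5 J/cm² at visit 1, 10 at visit 2 and 20 at visit 3. Dose and visit would then be completely aliased. The dose comparison, including the search for a biphasic response in the primary objective, could not be separated from anything that changes between visits.

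If it is carried out as randomisation, the sentence misdescribes the order in which patients meet the doses. Some will start at 20 J/cm², twice the per-session dose of the team's earlier study. Safety and tolerability at lower and higher doses open the primary objective, so the protocol should describe the exposure order correctly.

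**Working it through.** The protocol gives no figure on this point to reproduce. The check compares the statements, counts the orders and then prices the remedy.

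**1. Which term is the error?** One phrase points to escalation. Against it stand the rest of the same sentence, the randomisation before visit 1, the Lay Summary and the delivery instruction. No section makes a dose depend on tolerance of a lower one. Randomised order is the intended rule.

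**2. Counting the orders.** Three doses over three visits give 3! = 6 orders. Take n = 20 (Section 6) and assume that all six are permitted and equally likely.

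| Feature | Orders | Expected patients |
|---|---|---|
| Fully ascending (5-10-20) | 1 of 6 | 20 × 1/6 = 3.3 |
| 20 J/cm² first | 2 of 6 | 20 × 2/6 = 6.7 |
| 20 before 10 J/cm² | 3 of 6 | 20 × 3/6 = 10 |
| 20 before at least one lower dose | 4 of 6 | 20 × 4/6 = 13.3 |

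The chance that at least one patient starts at 20 J/cm², with independent draws, is 1 − (2/3)^20 = 0.9997.

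**3. Balance of the list.** If simple randomisation were used (an assumption, since the protocol does not fix the method), simulation gives first-visit dose counts that differ by 5 or more in about 43% of allocations, and at least one order unused in about 15%. With permuted blocks of six, 20 = 3 × 6 + 2, so each order is used by 3 or 4 patients, none is unused, and first-visit counts differ by at most 2.

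**4. Price of a visit term.** Take a within-patient model for AUC with patient and dose effects, with all visits completed (20 × 3 = 60 observations). The variance of the 20-versus-5 contrast is 2σ²/20 without visit. The ratio once visit is added is:

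- simple randomisation: median 1.03, 95th percentile 1.18;
- permuted blocks of six: median 1.003, maximum 1.008 over all 15 ways to fill the last two places.

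Residual degrees of freedom fall from 60 − 20 − 2 = 38 to 60 − 20 − 4 = 36, and the two-sided 5% critical t moves from 2.024 to 2.028.

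The starting point of 38 belongs to the patient-plus-dose model, which the protocol does not itself specify. A paired t-test on one pair of doses would have 20 − 1 = 19 degrees of freedom, so the proposed model is not short of them.

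**The case against.** The strongest reply is that the sentence corrects itself. The escalation term is followed at once by the statement that the order is randomised, two other places agree, and operators will follow a sequence fixed before visit 1. A reader might infer that staff and ethics reviewers are being told that every patient meets the lower doses before 20 J/cm². Read whole, the protocol does not tell them that, and the inference should not be pressed.

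A reader might also infer a safety failing. The documents do not support one. No step-up safeguard is promised, so none is lost. The rationale in the Background cites positive results elsewhere at 20 J/cm² and well above. The earlier study had no safety concerns over 46 exposures. Six sessions at 10 J/cm² come to 60 J/cm² per ulcer, against 5 + 10 + 20 = 35 J/cm² here. Pain is recorded after treatment at every visit. The between-visit safety form, completed at visits 2 and 3 only, is a separate matter that correcting this sentence would not change.

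A third point limits the remedy. The dose list could be read as 5 and 10 J/cm² in random order with 20 always last, which would also fit a varying order. The Lay Summary's statement that each visit delivers one of three randomised doses makes this unlikely but does not exclude it, and Figure 3 is not available to settle it. It would therefore be wrong to write into the protocol that one patient in three starts at 20 J/cm² before the sponsor has confirmed the permitted orders.

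Finally, model terms are often left to an analysis plan, and one may exist. That is fair for the visit term, which is offered as an improvement on the test that Section 7.2 names. It does not answer the contradiction in the allocation rule, which is protocol text.

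**Conclusion.** The point holds as a minor-to-moderate correction. The allocation rule contradicts itself, and the escalation term is the wrong half. That conclusion rests on the text alone. The expected counts rest on six equally likely orders, which the sponsor has yet to confirm, and the imbalance figures rest on simple randomisation, which the protocol does not specify.

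Complete aliasing of dose with visit is a consequence of following the wording literally. It should not be read as a description of the planned trial, since the rest of the protocol points the other way.

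The efficacy gain from balanced orders and a visit term is modest. Random order already protects the dose comparison from systematic bias by visit. The 23°C laboratory, morning visits, caffeine and smoking abstention, device calibration, stable drug doses, pre-light images and untreated hand further limit differences between visits. The case for the change is that it is almost free.

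**What to change.** 1. In Section 5, delete the escalation term and state: 'Each patient will be randomised to one of the permitted orders of 5, 10 and 20 J/cm² over the three visits.' List the permitted orders. The sponsor should confirm that all six are allowed and, if so, add that 20 J/cm² may be given at the first visit. If a label is wanted, the Background already has a suitable one in dose-ranging. The Lay Summary and the delivery instructions need no change.
2. Have the independent team member allocate orders from a pre-generated balanced list, for example permuted blocks of six if all six orders are permitted (3-4 patients per order).
3. In Section 7.2, replace the unadjusted t-test by a within-patient comparison of AUC between doses that includes a visit term.

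The cost is a wording change, a one-off list, two degrees of freedom and under 1% in variance with balanced orders. No patients, visits or measurements are added.

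### The safety record is limited to the time between visits, so the protocol makes no provision to record as safety a skin reaction during the light or the 90 minutes of imaging after it

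*Protocol*

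**What the plan says.** The primary objective (Protocol, section 4) opens with safety: "To assess the safety, tolerability, and efficacy (as assessed by surrogate measurement of skin perfusion and temperature) of our LLLT", in the context of dose finding at lower and higher irradiances.

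Section 5, Assessment of safety and tolerability, sets up two records.

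- **Safety.** "At each treatment study visit any safety issues (between visits) will be documented (e.g., new concerns about cutaneous changes". The next sentence places it: "This will be documented on a separate safety CRF at visits 2 and 3 (attached with this application").
- **Tolerability.** A 0-100 pain score, "directly attributed to the LLLT will be recorded immediately after treatment, on a separate tolerability CRF at visits 1, 2 and 3".

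Section 5, Assessment of efficacy, then describes the rest of the session. For perfusion: "We will perform LDI immediately before and after the light exposures and then every 10 minutes for 90 minutes". For temperature: "Standardised thermographic images shall be acquired immediately before and after the light exposures, and then every 10 minutes for 90 minutes". Both hands are imaged, and both measures are classed as efficacy. On the exposure itself, section 5 (Application of the LLLT device) says: "The LLLT will take approximately 10-15 minutes to complete".

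Section 7.1 refers in general terms to case report forms and safety/tolerability questionnaires. Section 8.4 halts the study if safety issues emerge but names no data source. Sections 8.1 to 8.6 contain no adverse-event recording procedure.

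**The concern.** The session is when a reaction to light can be seen directly and linked to one dose with least ambiguity. It is also the period that the stated safety window leaves out. If the protocol is followed as written, a report of no safety concerns at a given dose would not cover acute skin reactions at that dose.

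Two features of the design add weight. First, the earlier study's clean safety result came from 46 exposures at 10 J/cm². This study goes up to 20 J/cm², twice that dose, on a new device with sequential rather than simultaneous delivery, so the earlier result does not cover the present setup. Second, the efficacy surrogates are perfusion and temperature of the treated hand. A visible reaction could raise either and be counted as response in the area-under-the-curve analysis of section 7.2, with no planned safety entry beside it.

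An analysis plan could not repair this later, because it cannot analyse what no form asked for.

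**Working it through.** The protocol gives no figure to reproduce here. The check compares recording windows and counts exposures.

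**Inputs**

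- 20 patients (section 6), 3 visits each, one of three doses per visit (section 5).
- Light: 10 to 15 minutes (section 5, Application of the LLLT device).
- Imaging after light: immediately, then every 10 minutes for 90 minutes (section 5, Assessment of efficacy).
- Safety form: visits 2 and 3, about the interval between visits.
- Pain score: visits 1, 2 and 3, once, immediately after light.

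**Counts**

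- Exposures: 20 × 3 = 60, of which 20 at each dose.
- Session time with no safety record assigned: 10 + 90 = 100 to 15 + 90 = 105 minutes per visit.
- Image time points after light: 1 + 90/10 = 10 per session for each method, all classed as efficacy.
- Safety forms: 20 × 2 = 40 at most, each about a between-visit interval.

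**Cover of each period**

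| Period | Safety record assigned | Other record |
|---|---|---|
| During the light | 0 of 60 | Pain score at the end (tolerability) |
| The 90 minutes after light | 0 of 60 (0 of 20 per dose) | Perfusion and temperature images (efficacy) |
| After visits 1 and 2, until the next visit | 40 of 60 exposures | None |

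**Is the parenthesis a real limit or loose drafting?** The safety sentence begins by referring to every treatment visit, but the next sentence puts the form at visits 2 and 3 only. Those are exactly the visits preceded by an interval. A form meant to capture reactions in the session would also be needed at visit 1, where the tolerability form is used. The choice of visits therefore supports the literal, limiting reading. The two sentences still disagree on which visits apply and need reconciling.

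**What would have no designated place?** A reaction painful by the end of the light may show on the pain score, as tolerability. A reaction still present after visit 1 or 2 falls in the interval that the next safety form covers. What remains is a reaction that settles on site and is either painless or starts after the single pain reading.

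**With the window widened** to include the session at all three visits, cover would be 60 of 60 exposures, 20 of 20 per dose. The 20 visit-3 exposures would still have no safety record after the patient leaves. That is a separate matter.

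**The case against.** The strongest reply is that the forms cannot be read here. Both are attachments to the application, and the participant-flow figure is not shown. A reader might infer from the protocol that an in-session reaction would never be recorded. The documents do not support that: a form may carry an extra field, staff may note a reaction informally, or a patient may mention it at the next visit. What can be said is that the protocol text makes no provision for it.

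A reader might also infer that blistering or a lasting change at an ulcer would be missed. After visits 1 and 2 this does not follow, since anything persisting would reach the next safety form as a new skin concern.

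A third tempting reading is that an inflammatory reaction would appear only as benefit. That goes too far. Both hands are imaged on a timed schedule from before the light, with core and periphery readings at any ulcer or pitting scar, so an unusual local response would leave a trace against the untreated hand. It would not be identified as a safety event, but it would be on record. That a reaction would raise the surrogates is an inference about what could happen, not something the documents show.

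Finally, the halting rule in section 8.4 is not tied to the between-visit form. That is true, but it gives no means of collecting the information either.

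These points narrow the concern. None supplies the missing provision.

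**Conclusion.** The concern holds as a gap in the stated recording rule. Read as written, the protocol assigns an in-session skin-safety record to 0 of 60 exposures, 0 of 20 at each dose, while making safety by dose part of its primary objective. A per-dose safety conclusion would therefore not cover transient, painless or later-starting skin reactions during the light or the 90 minutes after it, and such a reaction could enter the efficacy results without being identified.

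This rests on three assumptions: all 20 patients complete all three visits; the between-visits limit is meant literally, as the choice of visits 2 and 3 suggests; and the unseen forms do not already ask about the session. If they do, the remaining error is that the protocol misdescribes them, and the text should be corrected to match. The size is a count of uncovered exposures. The documents give no basis for estimating how often such reactions occur. The change should be made: it bears on the primary objective and is cheap.

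**What to change.** 1. In section 5, extend the safety window to issues arising *during and between visits*.
2. Reconcile the statement that safety is documented at every treatment visit with the one that places the form at visits 2 and 3, and name the form for each visit.
3. At all three visits, add a brief skin-reaction entry before light, immediately after it, and at the 90-minute image: present or absent and, if present, site, onset and whether resolved by the end of the visit.
4. Tabulate these entries by dose, and flag affected sessions descriptively beside the perfusion and temperature results. Do not add an efficacy analysis that excludes those sessions. It would condition on a response to the light that may itself depend on dose, and could bias the within-patient dose comparison.
5. If the forms already hold such a field, correct the protocol text to match instead.

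**Cost.** A short extra entry at each of up to 60 sessions, made by staff who are already imaging the hand, and a protocol amendment with sponsor agreement and submission to the HRA and/or REC (sections 8.1 and 8.2). No extra visit is needed, and no dose, stopping or management rule changes.
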